12.2. Sample Size

12.2.1. Sample Size

12.2.1.1. Phase I Component: Between 1990 and 2007, we have treated 4260 patients with early stage prostate cancer (clinical stage T1 or T2, initial PSA <10 ng/ml, KPS 90 or 100) with protons only. The 3-year actuarial rectal/urinary grade 3 toxicity rate was $0.69\% \pm 0.15\%$ SE in this cohort. We will conservatively assume the standard toxicity rate p_0 to be 1% and set the unacceptable toxicity rate p_1 at 5%. Statistical error rates will be set at $\alpha=10\%$ for a false positive result (calling the treatment too toxic when it is not) and $\beta=10\%$ for a false negative result (accepting that the treatment is not too toxic when in reality it is) when using a one-sided test of significance. The sample size meeting these requirements is 105 patients.

12.2.1.2. Phase II Component: In the same patient cohort, the 3-year actuarial rate of biochemical progression free survival (bPFS) was 96%. We will conservatively assume the standard 3-year biochemical failure rate p_0 to be 5% and set the unacceptable failure rate p_1 at 10%. Statistical error rates for false positive and false negative results will again be set at 10%. The required sample size is 187 patients, which exceeds the required sample size for the toxicity endpoint. An additional 35% will be added to this number to guard against ineligible or evaluable cases, resulting in 288 patients. In order to be conservative the sample size for the Phase I/II study will be set to 300 patients.

12.2.1.3. Assuming we accrue the target goal of 187 evaluable patients, a 5% late toxicity rate equates to 9.34 patients with toxicity. If we have 9 or fewer patients with toxicity, the protocol therapy will be considered for further study. In addition, we must also meet the goals for tumor control. Assuming the target goal of 187 patients, tumor control will be considered acceptable if 12 or fewer patients have biochemical failure within the first three years. For the protocol therapy to be recommended for further study, both the toxicity and tumor control outcomes must be considered acceptable. This equates to 9 or fewer patients with late toxicity, and 12 or fewer patients with recurrence. If the study accrues more or less than 187 evaluable patients, these cut-off numbers will be adjusted accordingly.

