12.3. Stopping Rules for Excessive Acute Effects

The acute toxicity rate ($>=$ grade 2) in our previously treated patient with early stage prostate cancer was less than 15% (12.6% grade 2, 0.8% grade 3). We wish to ensure that the hypofractionation treatment does not increase the acute toxicity rate within the first three months after treatment commenced. The following table

gives the numbers of patients with acute toxicity (\geq grade 2) that are considered unacceptable at interim check points as calculated by the method of Fleming. For example, if there are 17 or more acute toxicities reported in the first 50 patients, the accrual will be stopped and the treatment protocol will receive a special review. Note that these are the first 50 patients entered (and eligible) consecutively onto the trial and not the first 14 patients for whom we have collected data up to three months. The last column lists the power to detect a 10% increase from an assumed 15% toxicity rate to 25% based on the number of patients available at each stage.

Number of Patients with acute Toxicity	Number of Patients Available	Power (%) (1- β)
15	50	20.7
22	100	75.6
30	150	92.1
35	187	97.6

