12.4 Patient Accrual

It is projected that there will be approximately a 2-month period with initial slow accrual (5-10 patients per month) at the beginning of this study to allow for establishing the procedures. After this initial period, it is projected that this study will accrue approximately 25 patients per month. At this rate, it will take 13 months to complete accrual. If the average monthly accrual is less than 15 patients per month, the study will be reevaluated with respect to feasibility.

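### Section 12.3 gives two stopping boundaries for acute toxicity in the first 50 patients: 17 in the worked example, 15 in the table; the table's 15 is evidently the intended one

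*Combined protocol and SAP*

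**What the plan says.** Section 12.3 sets a rule for excessive acute toxicity of grade 2 or higher. It introduces a table of event counts "that are considered unacceptable at interim check points as calculated by the method of Fleming". The rows are 15 events in 50 patients, 22 in 100, 30 in 150 and 35 in 187, with power 20.7%, 75.6%, 92.1% and 97.6%. The power column is described as the "power to detect a 10% increase from an assumed 15% toxicity rate to 25" percent, "based on the number of patients available at each stage".

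The worked example for the first look says that "if there are 17 or more acute toxicities reported in the first 50 patients, the accrual will be stopped" and that the protocol then receives a special review. The sentence after it explains which patients count and contrasts them with "not the first 14 patients for whom we have collected data up to three months".

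Section 12.3 states no alpha. For the sample size, Section 12.2.1.2 says "Statistical error rates for false positive and false negative results will again be set at 10" percent. Section 12.4 gives the expected pace: after a slow start, "it is projected that this study will accrue approximately 25 patients per month".

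**The concern.** The example and the table describe the same check point and give different boundaries. If 15 or 16 of the first 50 patients have an acute toxicity, the table calls the result unacceptable and the example lets accrual continue. The example is worded as an instruction, and no text gives the table precedence. The figure of 14 patients in the next sentence matches none of the check points (50, 100, 150, 187), so two numbers in the explanatory text do not fit the table.

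This is the only numeric rule in the document that halts accrual for toxicity. The limit of 9 late toxicities in Section 12.2.1.3 is a final decision criterion, and the six-monthly reports in Section 12.5.1 carry no threshold. If the conflict is found only when 15 or 16 events are on the table, the boundary will be chosen with the data in view.

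**Working it through.** **Inputs.** From Section 12.3: null rate 15%, alternative 25%, looks at 50, 100, 150 and 187 patients, tabled boundaries 15, 22, 30 and 35, example boundary 17. From Section 12.4: 25 patients per month. Assumed: one-sided alpha of 10%, borrowed from Section 12.2, and needed only in step 2.

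**Step 1: reproduce the power column.** Use the normal approximation without continuity correction at a true rate of 25%: power = 1 − Φ[(r − 0.25n) / √(n × 0.25 × 0.75)].

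| n | r | z | Power | Printed |
|---|---|---|---|---|
| 50 | 15 | (15 − 12.5)/3.062 = 0.816 | 20.7% | 20.7% |
| 100 | 22 | (22 − 25)/4.330 = −0.693 | 75.6% | 75.6% |
| 150 | 30 | (30 − 37.5)/5.303 = −1.414 | 92.1% | 92.1% |
| 187 | 35 | (35 − 46.75)/5.921 = −1.984 | 97.6% | 97.6% |

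All four agree. At n = 50, other boundaries give 31.2% (14), about 12.6% (16) and 7.1% (17). Only 15 yields the printed value, and this check needs no alpha. It also rules out a misread table entry.

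**Step 2: reproduce the boundaries.** Take the Fleming form r = nearest integer of [0.15n + z × √(187 × 0.15 × 0.85)] + 1, where the square root is 4.883.

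| One-sided alpha | Value before rounding | Boundaries |
|---|---|---|
| 10% | 13.76 / 21.26 / 28.76 / 34.31 | 15 / 22 / 30 / 35 |
| 5% | 15.53 / 23.03 / 30.53 / 36.08 | 17 / 24 / 32 / 37 |

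The 10% line is the table. The 17 of the example is the first entry of the 5% line, which agrees with no row of the table.

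**Step 3: exact binomial probabilities at the first look.**

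| True rate | P(15 or more) | P(17 or more) | P(15 or 16) |
|---|---|---|---|
| 15% | 0.53% | 0.07% | 0.46% |
| 20% | 6.1% | 1.4% | 4.6% |
| 25% | 25.2% | 9.8% | 15.4% |
| 30% | 55.3% | 31.6% | 23.7% |
| 35% | 81.2% | 61.1% | 20.1% |

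**Step 4: all four looks.** Carry the exact distribution through the looks, changing only the first boundary and keeping 22, 30 and 35.

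| True rate | Cumulative stop by 100 (15 vs 17) | Cumulative stop by 187 (15 vs 17) | Expected patients counted at stop, maximum 187 (15 vs 17) |
|---|---|---|---|
| 15% | 4.1% vs 3.9% | 11.7% vs 11.6% | 181.9 vs 182.3 |
| 25% | 79.1% vs 78.9% | 98.5% vs 98.5% | 100.0 vs 107.8 |
| 30% | 97.2% vs 97.1% | 99.99% vs 99.99% | 73.8 vs 85.7 |

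At 35% the expected numbers are 59.5 and 69.5.

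Given 15 or 16 events in the first 50, the boundary of 22 in 100 is reached anyway with probability 98.6% at a true 25% and 99.8% at 30%. The delay between these looks is 50 patients ÷ 25 per month = 2 months.

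**The case against.** The best case against is about weight. The operative statement is that the table lists the unacceptable counts; the 17 sits in an illustration, and the power figure beside 15 confirms the table. A careful reader would apply the table. At the planning rate of 15% the conflict zone is reached about once in 200 trials (0.46%). Overall detection and false stopping hardly move, and no endpoint, sample size or final decision rule is touched. A crossing suspends accrual for review and does not close the trial. Patients are also examined weekly during treatment.

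Most of this is correct and limits the size of the finding to a delay. It does not remove the contradiction: no text makes the table govern, and the example is phrased as an order to stop. The low probability at 15% is also a limited comfort, since the rule exists for the case in which the rate is higher.

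Two further points stand. The alpha in step 2, the formula and its rounding are not given in the document, so the idea that 17 was carried over from a 5% calculation is an inference; step 1 is sufficient without it. And the expected numbers in step 4 count only patients evaluated at a look. Acute toxicity is judged over three months, so if accrual is not paused while the window runs, about 3 × 25 = 75 more patients could be enrolled before a look is complete, under either boundary.

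**Conclusion.** The concern holds. Section 12.3 gives two boundaries for the same safety look, and the table's 15 is the intended one on the evidence of its own power column. The ambiguity matters only with 15 or 16 events: probability 15.4% at a true 25%, 23.7% at 30%, 20.1% at 35%, and 0.46% at 15%. Its cost is a stop postponed from 50 to 100 patients, about two months at full projected accrual. On average that is 8 to 12 more patients counted at the stop for true rates of 25% to 35%. It is not a loss of overall detection. These figures assume independent patients with a common toxicity rate and the other three boundaries as tabled. The correction is required because a stopping rule must return one answer at each look, and the choice should be made before the first look.

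**What to change.** In Section 12.3, change the example's boundary from 17 to 15 and, in the sentence after it, change 14 patients to 50. The table, sample size and conduct stay as they are, so the cost is two numbers in two sentences. State the alpha used for the boundaries at the same time if it was indeed 10%.

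If the sponsor did intend 17, the whole table has to move to the matching set, 17/24/32/37, and the power column has to be recalculated.

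Optionally, label the power column as a normal approximation, or replace it with the exact single-look values for the tabled boundaries: 25.2%, 78.9%, 93.7% and 98.3%.

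### Section 12.3 counts only eligible patients toward the acute-toxicity stopping boundary, so toxicity in a treated but ineligible man does not reach the one formal acute-safety rule

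*Combined protocol and SAP*

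**What the plan says.** Section 12.3 aims to ensure that the new schedule "does not increase the acute toxicity rate within the first three months after treatment commenced". Its table sets four looks, at 50, 100, 150 and 187 patients, with 15, 22, 30 and 35 patients with grade 2 or higher toxicity as the unacceptable counts. The last column is the "power to detect a 10% increase from an assumed 15% toxicity rate to 25% based on the number of patients available at each stage". The worked example in the text gives a different first boundary: "if there are 17 or more acute toxicities reported in the first 50 patients, the accrual will be stopped".

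On who is counted, the section says: "Note that these are the first 50 patients entered (and eligible) consecutively onto the trial". The sentence goes on to say that a look is not defined by whose three-month data happen to be in. It refers there to 14 patients, which matches none of the four looks.

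Section 12.2.1.2 requires 187 patients for the 3-year biochemical endpoint and then states: "An additional 35% will be added to this number to guard against ineligible or evaluable cases, resulting in 288 patients". I read the last category as inevaluable cases. The allowance is one pooled figure and is not split between ineligible and inevaluable. The total is then rounded up: "In order to be conservative the sample size for the Phase I/II study will be set to 300 patients".

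Section 12.5.1 adds six-monthly interim reports that include toxicity. They are not stated to be limited to eligible patients, and no boundary or action is attached to them.

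**The concern.** The purpose of the rule is to judge the treatment, and every man who receives that treatment is informative about its acute toxicity. Eligibility matters for judging tumour control in low-risk disease. It is not an obvious reason to leave a treated man out of a safety count.

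Some exclusions in section 3.2 (inflammatory bowel disease, concurrent Coumadin, previous pelvic irradiation) plausibly bear on bowel or urinary toxicity. If such a man were treated in error, his reaction is one that a safety rule should register.

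Two things follow from the wording. Events in treated but ineligible men cannot contribute to crossing the boundary, and more men than the table shows are treated before each look. No other stopping rule in the plan covers these men.

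**Working it through.** **Inputs.** Looks at n = 50, 100, 150 and 187, boundaries 15, 22, 30 and 35, and acute toxicity rates of 15% (assumed) and 25% (to be detected), all from section 12.3. Pooled allowance of 35% on 187, from section 12.2.1.2. Steady accrual of about 25 per month, from section 12.4. The share d of treated men later ruled ineligible is not in the documents. I assume 5% to 20% and show 35% as a ceiling.

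**Reproducing the plan's figures.**
- Allowance: 187/(1 − 0.35) = 287.7, so 288, as stated.
- Power, by the normal approximation without continuity correction, 1 − Φ[(r − 0.25n)/√(n × 0.25 × 0.75)]. For 15 of 50 this is 1 − Φ(2.5/3.06) = 20.7%. The other three looks give 75.6%, 92.1% and 97.6%. All four match the table. Exact binomial values are 25.2%, 78.9%, 93.7% and 98.3%.
- The tabulated 20.7% corresponds to 15 of 50. The text's 17 of 50 would give 7.1% by the same formula (9.8% exact). This shows that text and table are not interchangeable; it does not settle which was intended.

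**Effect of counting eligible men only.** Men entered and treated when the look is reached = n/(1 − d). Uncounted men = n/(1 − d) − n. Uncounted events = uncounted men × 0.15 or × 0.25. Delay = uncounted men/25 months.

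| d | Look at 50: entered | Uncounted events (15%, 25%) | Delay, months | Look at 187: entered | Uncounted events (15%, 25%) | Delay, months |
|---|---|---|---|---|---|---|
| 5% | 52.6 | 0.4, 0.7 | 0.1 | 196.8 | 1.5, 2.5 | 0.4 |
| 10% | 55.6 | 0.8, 1.4 | 0.2 | 207.8 | 3.1, 5.2 | 0.8 |
| 20% | 62.5 | 1.9, 3.1 | 0.5 | 233.8 | 7.0, 11.7 | 1.9 |
| 35% (ceiling) | 76.9 | 4.0, 6.7 | 1.1 | 287.7 | 15.1, 25.2 | 4.0 |

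Example at d = 10%: 50/0.90 = 55.6 entered, 5.6 uncounted, 5.6 × 0.15 = 0.8 and 5.6 × 0.25 = 1.4 events, 5.6/25 = 0.2 months.

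The tabulated power does not change, because it is conditional on the number counted.

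**The case against.** The strongest reply is that few men are likely to fall in this gap and that they are not unmonitored. Histology review at the centre is an eligibility criterion (3.1.3) and a pretreatment step (4.1.5). Nodes are assessed on the planning CT before treatment (4.1.2). Colitis and Coumadin are entry exclusions (3.2.8, 3.2.9). A man found ineligible before his first fraction would not be counted under the proposed change either. All patients are examined weekly during treatment (6.4.1, 11.2.1), toxicity is assessed at every follow-up visit (11.1), and the six-monthly reports may include ineligible men. This stands: what is missing is a boundary for these men, not any record of them.

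Scale also favours the plan. At 25 per month, if accrual continues, about 3 × 25 = 75 further men enter during the three-month window that follows any look's last entry. A delay of 0.1–0.2 months is small beside that.

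It can also be said that the 15% benchmark belongs to a defined population, so men outside the criteria should not be set against it. This carries some weight, but section 12.3 describes the benchmark only as earlier early-stage patients. The institutional cohort in section 12.2.1.1 is described by stage, PSA and performance status, with no mention of the other exclusions. The documents therefore do not show that an eligible-only count is the closer match.

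Two stronger readings are tempting. A reader might infer that 35% of treated men would bypass the rule. The documents do not support that. The allowance pools ineligible and inevaluable cases for a 3-year endpoint, whereas section 12.3 excludes on eligibility alone and counts by order of entry, so an eligible man later lost to PSA follow-up is still counted. A reader might also infer that events could be removed by eligibility rulings made once toxicity is known. In an open single-arm trial with no stated time for such rulings this is possible, but nothing in the documents describes it, and the rest of the quoted sentence is aimed at preventing selection by data availability.

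**Conclusion.** The gap is real and rests on explicit wording: toxicity in a treated but ineligible man is outside the only formal acute-toxicity boundary, and each such man moves the next look back by one entry.

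Its size depends on a share that the documents do not give. At an assumed 5–10% it is modest: about 3–6 uncounted men at the first look and about 10–21 at the last, where the delay is 0.4–0.8 months. The 35% row is an upper bound that would require no inevaluable patients at all and every ineligible man to have been treated. It should not be quoted as the expected effect. The event figures also assume that ineligible men have the same 15% or 25% toxicity rate as the others.

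This is a cheap improvement to a safety rule, not a flaw that invalidates it.

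**What to change.** In section 12.3, define the looks as the first 50, 100, 150 and 187 consecutive patients who received at least one protocol fraction, regardless of later eligibility findings. In section 12.5.1, add a separate tabulation of acute events in ineligible patients to the six-monthly report.

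The cost is a sentence in each section. Weekly examinations and the 3-month toxicity evaluation already supply the data. The downside is that a few off-criteria men may raise the observed rate slightly and so bring about an accrual stop and special review that an eligible-only count would not have triggered. The separate tabulation lets that review see whether this happened.

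This change does not in itself require different boundary counts, but they cannot simply be carried over. The text's 17 of 50 and the table's 15 of 50 contradict each other, and the mention of 14 patients fits no look. These must be reconciled in the same edit, and the power column checked against the result.

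### The power column of the acute-toxicity stopping table (Section 12.3) is an uncorrected normal approximation: against exact power for the table's limits it is 4.5 and 3.3 points low at the first two looks, and its first figure fits neither limit given for 50 patients

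*Combined protocol and SAP*

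**What the plan says.** Section 12.3 gives a stopping table for acute toxicity of grade 2 or higher. The limits are 15 of 50, 22 of 100, 30 of 150 and 35 of 187 patients. They are counts that "are considered unacceptable at interim check points as calculated by the method of Fleming". Reaching a limit stops accrual and triggers a special review.

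The last column gives power of 20.7, 75.6, 92.1 and 97.6%. Of this column the text says "The last column lists the power to detect a 10% increase from an assumed 15% toxicity rate to 25" percent, and it ties each figure to the patients available at that stage. It does not call the figures approximate, and it does not say whether they are per-look or cumulative. The section states no significance level and no probability of stopping when toxicity is acceptable.

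The worked example describes stopping "if there are 17 or more acute toxicities reported in the first 50 patients". The table's limit for the same 50 patients is 15.

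**The concern.** The rule acts on a count, so its power is a binomial tail probability that can be calculated exactly. The printed column does not equal that probability at the table's limits, and the largest gaps are at the two earliest looks. A second difficulty lies under the first: the section gives two different limits at 50 patients, so the first entry cannot be checked against a single rule.

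The table is the plan's only statement of how this stopping rule performs. Whoever conducts the special review would use it to judge how likely the rule is to catch a rise to 25%, and would find nothing on how often it would halt accrual at 15%.

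**Working it through.** **Inputs, all from Section 12.3.** Rates of 15% and 25%; limits r = 15, 22, 30, 35 at n = 50, 100, 150, 187; stop at r or more, the direction used in the worked example.

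**Step 1: reproduce the stated column.** Take each look alone, with no continuity correction, at a true rate of 0.25:

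power = 1 − Φ[(r − 0.25n) / √(n × 0.25 × 0.75)]

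| n | r | 0.25n | SD | z | Result | Stated |
|---|---|---|---|---|---|---|
| 50 | 15 | 12.5 | 3.062 | 0.816 | 20.71% | 20.7% |
| 100 | 22 | 25 | 4.330 | −0.693 | 75.58% | 75.6% |
| 150 | 30 | 37.5 | 5.303 | −1.414 | 92.14% | 92.1% |
| 187 | 35 | 46.75 | 5.921 | −1.984 | 97.64% | 97.6% |

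All four rows match. The first entry was therefore computed from 15; the same formula with 17 gives 7.1%. This shows how the column was made. It does not show which limit is intended.

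**Step 2: exact power at a true 25%.** Per-look power is P(X ≥ r) for X ~ Binomial(n, 0.25). Cumulative power is the probability of having reached a limit at this or an earlier look, found by exact recursion over the four looks.

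| n | Limit | Stated | Exact, per look | Shortfall (points) | Exact, cumulative | Shortfall (points) |
|---|---|---|---|---|---|---|
| 50 | 15 | 20.7% | 25.2% | 4.5 | 25.2% | 4.5 |
| 100 | 22 | 75.6% | 78.9% | 3.3 | 79.1% | 3.5 |
| 150 | 30 | 92.1% | 93.7% | 1.6 | 94.3% | 2.2 |
| 187 | 35 | 97.6% | 98.3% | 0.7 | 98.5% | 0.9 |

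Putting a continuity correction into the formula of Step 1 gives 25.7% and 79.1% at the first two looks, so its omission explains nearly all of the gap. Accumulating over looks adds at most 0.6 points (94.3 − 93.7).

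**Step 3: could another exact reading rescue the column?** If stopping needed more than r events, exact per-look power would be 16.3, 71.4, 90.9 and 97.4%. That is close at the last look but 4.4 and 4.2 points below the stated values at the first two.

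**Step 4: the other limit at 50 patients.** With 17 or more, exact power at the first look is 9.8%, so the stated 20.7% would be 10.9 points too high. With 17 at the first look and the table's limits afterwards, cumulative power is 9.8, 78.9, 94.3 and 98.5%.

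**Step 5: probability of stopping at a true 15%.** The same recursion gives:

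| Limits | 50 | 100 | 150 | 187 |
|---|---|---|---|---|
| 15/22/30/35 | 0.5% | 4.1% | 7.4% | 11.7% |
| 17/22/30/35 | 0.1% | 3.9% | 7.3% | 11.6% |

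At the acute toxicity rate reported in the same section (12.6% grade 2 + 0.8% grade 3 = 13.4%), the overall probability with the table's limits is 3.5%.

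**The case against.** The strongest reply is that the error is small and in the safe direction. With the table's limits the rule catches a rise to 25% slightly more often than the plan says, and the gap at the last look is 0.7 points. No limit, sample size or patient's care depends on the column. That stands, and it keeps the point modest.

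It can also be said that the wording about each stage reads naturally as per-look power. That stands too. Ignoring earlier looks is not the fault, and it accounts for little of the gap.

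A reader might infer that the rule protects patients less well than claimed. The documents do not support this for the table's limits, where every exact figure is above the stated one. Only at the first look, and only if 17 applies, is the stated power too high.

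A reader might also infer that the rule breaks a 10% false-stop level. The limits do fit Fleming's formula with an assumed one-sided 10% level: 0.15n + 1.2816 × √(187 × 0.15 × 0.85) gives 13.76, 21.26, 28.76 and 34.31, and these rounded to the nearest integer, plus 1, are 15, 22, 30 and 35. But that level is inferred. Section 12.3 states none, and the 10% error rates in Section 12.2.1 are set for other endpoints. Besides, 15% is a cautious reference rate (the section puts the earlier rate below it), and crossing a limit leads to a review, so a false stop can be examined. The 11.7% is useful information and not a breach of a stated level.

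**Conclusion.** The concern holds as a limited arithmetic error. The column is a per-look normal approximation without continuity correction and is not labelled as one. For the table's limits, read as that count or more, it understates exact power at a true 25% by 4.5 and 3.3 points at the first two looks and by 1.6 and 0.7 points at the last two. On the cumulative scale the shortfalls are 4.5, 3.5, 2.2 and 0.9 points.

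The sign at the first look depends on a conflict that the plan must settle: 20.7% is too low if the limit is 15 and too high if it is 17. Since it is wrong either way, reconciling the two numbers will not by itself repair the column.

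These figures assume independent patients with a common toxicity rate, and looks at exactly the four listed sample sizes.

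**What to change.** 1. Reconcile the worked example's 17 with the table's 15 at 50 patients. The plan's authors must say which applies; this review takes no position.
2. State in the table whether each limit means that count or more, as the example implies.
3. Replace the power column with exact binomial stop probabilities at a true 25% for the reconciled limits, labelled per-look or cumulative. The values for both candidate limits are in the working above.
4. Beside it, report the exact cumulative stop probability at a true 15%: 0.5, 4.1, 7.4 and 11.7% with the table's limits, or 11.6% overall if 17 applies at the first look. If a false-stop level was intended, state it.

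This point calls for no change to any stopping limit beyond settling that conflict. The cost is a few lines of exact calculation and one table edit, with no additional patients and no new procedures.
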